2.4.2 Pharmacodynamic Endpoints

The PD endpoints are calculated from the mean of the triplicate continuous 12-lead ECG data as:

1. $dQTcF$ – baseline-adjusted QT interval corrected by Fridericia's formula ($QTcF$);
2. $ddQTcF$ – time-matched, placebo-corrected, baseline-adjusted $QTcF$, which is calculated as the $dQTcF$ minus the time-matched mean $dQTcF$ of all placebo subjects at each postdose time point ($ddQTcF=[dQTcF(\text{active dose groups})-\text{mean } dQTcF(\text{placebo})]$);

The primary study endpoint is the $dQTcF$ matched to the plasma concentration of moxidectin collected at the same time point.

Analogous-derived exploratory endpoints are also calculated for heart rate (HR), and duration of PR, RR, and QRS interval parameters.

The ECG morphologic changes data are also considered an exploratory endpoint.

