3.2 Sample Size Considerations

The sample size of 60 subjects (10 subjects each in 6 treatment groups) is considered adequate to explore the effects of moxidectin on the corrected QT interval (QTc), as this design will yield 900 QTc-PK pairs in total. Additional subjects may be enrolled as alternates in this study should a subject choose to withdraw consent before study drug administration. Alternate subjects will remain in the clinical research unit (CRU) from Check-in until all subjects due to be dosed have completed dosing. Subjects who withdraw after dosing will not be replaced.

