3.3 Study Design

This is a randomized, single-center, double-blind, placebo-controlled, parallel-group study in which healthy male subjects will be randomly assigned to one of the following treatments:

- Treatment 1: moxidectin 4 mg (n = 10)
- Treatment 2: moxidectin 8 mg (n = 10)
- Treatment 3: moxidectin 16 mg (n = 10)
- Treatment 4: moxidectin 24 mg (n = 10)
- Treatment 5: moxidectin 36 mg (n = 10)
- Treatment 6: matching placebo (n = 10)

Subjects will be screened for eligibility up to 28 days before randomization. Subjects who meet all of the inclusion and none of the exclusion criteria will be admitted to the CRU on Day -1 (not less than 12 hours before scheduled dosing). Subjects will remain in the CRU for at least 72 hours after dosing and will return to the CRU for further assessment on Days 8, 15, and 22, and Week 12. At Week 8, subjects will be contacted via telephone for recording of AEs and concomitant medication use.

Randomized subjects will be assigned unique subject numbers in sequential order based on their order of qualification. Randomization will take place before dosing on Day 1, with equal random assignment to each treatment. Subjects are considered as enrolled once randomized.

The duration of participation in the study for each subject will be up to approximately 112 days, including Screening.

For purposes of statistical analysis, this study is divided into 2 study periods:

- Period 1: Commences at Screening and will finish on Day 22. The study blind will be maintained during this study period. After the last subject has completed the study through Period 1, the blind will be broken and the data from Period 1 will be analyzed.
- Period 2: Runs from Day 23 to Week 12. Data from Period 2 will be analyzed after all subjects have completed the study through Week 12. Data for some subjects may be collected during Period 2 after the blind has been broken.

The overall schedule of events is provided in Table 1 and the Period 1, Day -1 to Day 4 schedule of events is provided in Table 2.

Table 1. Overall Schedule of Events

Assessment	Screening D-28 to D-2	Period 1									Period 2										
		D-1	Baseline D1 (Predose)	D1	D2	D3	D4	D8	D15	D22	W8	W12 ^f									
Outpatient visit	X	Refer to Table 2: Schedule of Events for Period 1 (Day -1 to Day 4)									X	X	X		X						
Informed consent	X																				
Telephone call																				X	
Inclusion/exclusion criteria review	X																				

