8.3 Statistical Analyses

Primary Analysis

The relationship between time-matched, baseline-adjusted QTcF (dQTcF) and moxidectin concentrations will be investigated by linear mixed-effects modeling. The ddQTcF value will be calculated as the placebo-corrected dQTcF estimated from the model.

Before modeling, the concentration-ddQTcF relationship will be explored graphically to determine the presence of hysteresis. Hysteresis will be assumed if, on average (or median), there are at least 3 time points with ddQTcF >5 msec and the time to maximum observed plasma concentration (T_{max}) and the time of maximal ddQTcF (U_{max}) differ by 30 minutes or more and the 1-sided, 1-sample Wilcoxon test for the difference between ddQTcF at T_{max} and at U_{max} is significant at the 1% level. If hysteresis is present, the possibility of fitting a population PK model with an effect compartment will be explored.

The primary analysis will be provided for the ECG population using a mixed-effects model with dQTcF as the dependent variable and treatment (active and placebo), time point, and treatment by time point interaction as the independent variables with baseline QTcF as a covariate and time-matched concentrations of moxidectin (observed if hysteresis is not present; predicted from the effect compartment if hysteresis is present) as a covariate with random effects of intercept and slope. Concentrations of zero will be used for the placebo treatment. A spatial power law covariance structure (a time-dependent first-order autoregressive covariance designed for unequally-spaced time points) will be used. If the model does not converge then unstructured (UN) or compound symmetry (CS) structures will be assessed, in that order. The model will be used for predicting population average and 90% 2-sided bootstrapped CI of the baseline-adjusted difference (ie, ddQTcF) between active and placebo at each time point bound at clinically relevant concentrations. The bootstrap method will be based on percentile CI using the 5th and 95th percentiles in the resampling distribution using 1000 iterations.

The criterion for negative QT assessment will be the upper bound of the 2-sided 90% bootstrapped CI for ddQTcF being below 10 msec at the largest geometric mean C_{max} value. In addition, the significance and magnitude of parameter estimates of the treatment covariate (active vs. placebo) will be considered.

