At the request of the United States Food and Drug Administration, the primary endpoint in the study has been updated to dQTcF and this is the dependent variable in the primary analysis, which includes plasma concentrations as covariates with random slope and intercept as well as treatment and time point as categorical independent variables. However, in addition to obtaining the plasma concentration intercept and slope estimates, the estimated dQTcF values from the primary analysis will be compared by calculating the differences overall and at each time point between the active treatment and placebo, resulting in estimates of ddQTcF, which will be presented. In addition, a secondary analysis with ddQTcF as the dependent variable will be performed, as is typical and well understood, to assess correlation and overall profile of ddQTcF and plasma concentrations. We believe it is important to do these analyses in addition to the primary analysis, because the dQTcF analysis could yield a spuriously positive or negative regression slope based on the relationship between the well-known spontaneous circadian change in dQTcF and the concentration-time profile of the investigational drug. For example, if the early to midday circadian increase in dQTcF concurred with a rise in plasma concentration of moxidectin, this could create the appearance of a positive relationship that might exceed the upper confidence boundary of 10 msec within the drug's clinically-expected concentration range. Converse timing between circadian change and plasma concentration change could produce the opposite effect. In the ddQTcF analysis, the placebo group's circadian change largely eliminates this type of spurious observation. Thus, in addition to examining the dQTcF model, if the primary analysis produces a significantly positive or negative regression slope, we will also examine the relationship between the investigational drug's plasma concentration-time course in relationship to the circadian change of dQTcF in the placebo group, to determine if a positive or negative correlation could have affected the dQTcF-plasma concentration relationship.

The relevant SAS code statements are:

```
PROC MIXED DATA = DATA;  
  CLASS SUBJID TRT ATPTN;  
  MODEL dQTcF = BASE TRT ATPTN TRT*ATPTN CONC /SOLUTION  
RESIDUAL OUTP=PRED;  
  RANDOM INTERCEPT CONC / SUBJECT = SUBJID;  
  REPEATED ATPTN / type=SP(POW) (ATPTN) SUBJECT=SUBJID;  
  LSMEANS TRT TRT*ATPTN /DIFF ALPHA=0.1 CL at CONC=xx.x;  

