  LSMEANS TRT TRT*ATPTN /DIFF ALPHA=0.1 CL;  
RUN;
```

In the above statements:

- TRT represents the treatment (active or placebo);
- ATPTN represents the postdose nominal time point;
- BASE represents the baseline value for QTcF;
- CONC represents measured plasma concentrations of moxidectin;

- SP(POW) is a spatial power law covariance structure (a time-dependent first-order autoregressive covariance designed for unequally-spaced time points), if the model does not converge then unstructured or compound symmetry structures will be assessed, in that order;
- LSMEAN differences between the treatments at the Geometric C_{\max} value and at the average concentration value, where xx.x represents the largest geometric mean C_{\max} value among the doses, most likely for the 36-mg dose, will be provided.

Model assumptions will be reviewed with plots of standardized residuals versus fitted values and normal Q-Q plots of the standardized residuals. If nonlinearity is present, a log linear and/or maximum effect (E_{\max}) or other model will be considered.

Similar analyses will be repeated for HR, PR, and QRS, however, bootstrap percentiles will be based on the 2.5th and 97.5th percentiles, corresponding to a 2-sided 95% CI rather than the 2-sided 90% CI.

Secondary Analysis: Pharmacokinetic/Pharmacodynamic Analyses

To evaluate the relationship between placebo-corrected mean change from Baseline in QTcF (ie, ddQTcF) versus plasma concentrations of moxidectin for all subjects in the PK/PD population, both graphical and mixed-effects analyses of plasma concentration of ddQTcF versus plasma concentration of moxidectin will be performed. The mixed-effects model will be used to account for the clustering effects within each subject at different time points. The mixed-effects model will contain ddQTcF as the dependent variable and include the corresponding time-matched plasma moxidectin concentrations as the independent variable. The mixed-effects model will be used to estimate, for all subjects, the predicted population mean ddQTcF and its corresponding upper 95% 1-sided (equivalent to the upper 90% 2-sided) CI over a range of observed plasma concentrations. A negative result (ie, the model indicates no plasma concentration effect) is a slope of approximately zero.

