The adequacy of the linear assumption between ddQTcF and plasma concentrations will be determined by adding a quadratic term to the mixed-effects model. If the quadratic term is different than zero, having $P < 0.05$, and Akaike's information criterion (AIC) is smaller in comparison with the linear model's AIC, then a quadratic term may be added. In addition, a transformation of the concentrations (eg, $\log[C/LLOQ]$, where LLOQ is the lower limit of quantitation of the assay and all values below the LLOQ are replaced with the LLOQ) may also be assessed. The best model fit will be determined by the lowest AIC.

The predicted mean expected ddQTcF and the 90% 2-sided CI will be calculated using the estimates of the slopes from the mixed-effect models, for all subjects, at relevant concentration levels (ie, the mean maximum plasma concentration under each dose level).

The relevant SAS code statements are:

```
PROC MIXED DATA = DATA;  
  CLASS SUBJID;  
  MODEL ddQTcF = CONC /SOLUTION OUTPM=PRED ALPHA=0.05;  
  RANDOM INTERCEPT CONC / TYPE=UN SUBJECT = SUBJID;  
RUN;
```

In the above statements:

- CONC represents the measured plasma concentrations of moxidectin;
- Type=UN means an unstructured covariance matrix, which is used for the correlated random effects (INTERCEPT and CONC). If the model does not converge other covariance structures will be investigated.

A plot will be provided to show CI of each treatment using the following model, adding in the treatment variable as follows:

```
PROC MIXED DATA = DATA;  
  CLASS SUBJID TRT;  
  MODEL ddQTcF = CONC TRT/SOLUTION OUTP=PRED;  
  RANDOM INTERCEPT CONC /TYPE=UN SUBJECT = SUBJID;  
RUN;
```

Where TRT represents the individual treatments (moxidectin 4 mg, moxidectin 8 mg, moxidectin 16 mg, moxidectin 24 mg, and moxidectin 36 mg).

A plot of the observed median-decile drug concentrations and associated mean ddQTcF (90% CI) together with the mean model-predicted ddQTcF will be used to evaluate the adequacy of the model fit to the assumption of linearity and the impact on quantifying the concentration response relationship.

Categorical QTc Findings

Categorical summaries using the largest postdose QTcF and largest change from Baseline (dQTcF) will be performed to determine the number and percentage of subjects, by treatment, who meet each of the following criteria:

- Result ≤ 450 msec;
- Result > 450 and ≤ 480 msec;
- Result > 480 and ≤ 500 msec;
- Result > 500 msec;
- dQTcF ≤ 30 msec;

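### Both secondary ddQTcF models omit the baseline QTcF covariate that the primary model carries, so chance baseline imbalance shifts their predictions by roughly 0.4 to 3 msec (SD, under assumed inputs)

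*SAP*

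**What the plan says.** All of this is in the SAP.

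- **Primary model (Section 8.3, Primary Analysis).** dQTcF is modelled "with baseline QTcF as a covariate". The code agrees: "MODEL dQTcF = BASE TRT ATPTN TRT*ATPTN CONC /SOLUTION", where "BASE represents the baseline value for QTcF".
- **Secondary prediction model (Section 8.3, Secondary Analysis).** The fixed part is concentration alone: "MODEL ddQTcF = CONC /SOLUTION OUTPM=PRED ALPHA=0.05". From this model the plan wants predicted mean ddQTcF with a two-sided 90% CI at the mean maximum concentration of each dose. It reads a slope near zero as a negative result.
- **Secondary plot model (same section).** The individual dose groups are added, but again no baseline: "MODEL ddQTcF = CONC TRT/SOLUTION OUTP=PRED".
- **How ddQTcF is formed (Section 2.4.2).** Each active subject's change from baseline is taken "minus the time-matched mean $dQTcF$ of all placebo subjects at each postdose time point". This is a raw mean with no covariate adjustment.
- **Who is in the secondary models (Section 5.4).** The PK/PD population is defined by time-matched concentrations on active moxidectin. Placebo therefore enters only through the subtracted mean.
- **Group sizes (Section 3.2).** There are "10 subjects each in 6 treatment groups", so 50 active and 10 placebo subjects.

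The SAP gives no reason for adjusting one analysis and not the other.

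**The concern.** Subtracting baseline does not remove its influence. A subject whose baseline QTcF is high by chance tends to show a fall afterwards, so change from baseline is negatively correlated with baseline. The primary model deals with this through its baseline term. In the secondary models nothing does, although baseline QTcF is already derived for every subject in the ECG population.

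Two distinct consequences need to be kept apart:

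1. **A shift.** If the 10 placebo subjects happen to start higher or lower than the active subjects, part of that difference regresses to the mean and appears as an offset in ddQTcF. It goes into the intercept and so into every prediction.
2. **Lost precision.** Baseline variation among the active subjects is left in the residual, which makes the model-based CI somewhat wider than necessary.

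Section 8.3 introduces the ddQTcF analysis because circadian change could distort the primary slope. If the two analyses also differ in baseline adjustment, a disagreement between them is harder to attribute to that cause.

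**Working it through.** **The plan's own figure.** The only sample-size figure in the SAP is 900 QTc-PK pairs: 60 subjects × 15 time points (baseline plus 14 postdose) = 900, which reproduces. The secondary models can use at most 50 × 14 = 700 postdose active pairs.

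**Assumed inputs.** The SAP gives no QTcF variability. Assume a between-subject SD s of 12 to 20 msec and a within-subject SD e of 5 to 10 msec, with the baseline-to-postdose correlation the same at all time points.

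**Formulas.**
- Slope of change on baseline: b = −e²/(s² + e²).
- Baseline SD: √(s² + e²).
- SD of the chance shift, 50 active v 10 placebo: |b| × baseline SD × √(1/50 + 1/10), where the root is 0.346. For one dose group v placebo the root is √(1/10 + 1/10) = 0.447.
- Widening of the subject-level SE without baseline: 1/√(1 − |b|).

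| s / e (msec) | b | Baseline SD | Shift SD, all active | Shift SD, one dose | Subject-level SE wider by |
|---|---|---|---|---|---|
| 20 / 5 | −0.059 | 20.6 | 0.42 | 0.54 | 3% |
| 16 / 7 | −0.161 | 17.5 | 0.97 | 1.25 | 9% |
| 12 / 10 | −0.410 | 15.6 | 2.22 | 2.86 | 30% |

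For the last row: b = −100/244 = −0.410, and 0.410 × 15.6 × 0.346 = 2.2 msec.

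**Cross-check with other assumptions.** Take a baseline SD of 18 msec and a correlation r of 0.5 to 0.9. The raw baseline imbalance has SE 18 × 0.346 = 6.2 msec. Only the fraction (1 − r) reaches ddQTcF: 6.2 × 0.5 = 3.1 down to 6.2 × 0.1 = 0.6 msec. The two sets together give roughly 0.4 to 3 msec.

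**Simulation of the prediction at the 36-mg geometric mean Cmax.** There were 3,000 trials per scenario, with no true effect, 14 postdose times, a random intercept only, known variances, no circadian term and Cmax proportional to dose. Entries are the 90% CI half-width / true SD of the prediction, in msec.

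| s / e | No baseline | Baseline, evaluated at active mean | Baseline, evaluated at placebo mean |
|---|---|---|---|
| 20 / 5 | 1.73 / 2.21 | 1.71 / 2.20 | 1.75 / 2.18 |
| 16 / 7 | 2.42 / 3.17 | 2.31 / 3.15 | 2.38 / 3.05 |
| 12 / 10 | 3.47 / 4.59 | 3.02 / 4.42 | 3.10 / 3.80 |

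- **Width.** 1.73/1.71, 2.42/2.31 and 3.47/3.02 give a CI about 1%, 5% and 15% wider without baseline. Evaluated at the placebo mean, the adjusted interval gives back part of this gain (in the first scenario all of it), because it also carries the uncertainty of the estimated baseline slope.
- **Accuracy.** At the placebo mean the true SD falls in all three scenarios. At the active mean it barely moves, because the placebo imbalance is still there.
- **Slope.** With baseline added, the true SD of the slope falls by 0.6%, 2.3% and 9.1% (2.270 to 2.257, 3.130 to 3.057 and 4.395 to 3.993, on the scale of 36 times the slope). This reflects imbalance between dose groups. A constant placebo offset contributes nothing.
- **Coverage of the nominal 90% CI.** It is 54% to 57% without baseline and 51% to 59% with it. A joint dQTcF model that includes the placebo data and baseline covers 89% to 91%, with half-widths of 3.15 to 5.24 msec.

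**The case against.** The strongest case against is that nothing here is an error or a contradiction. The secondary text and code agree with each other. The analysis is supportive, and its stated purpose is to describe the concentration–ddQTcF profile and guard against circadian artefact, which subtracting the time-matched placebo mean does without a baseline term. Baseline is a triplicate mean, which raises the correlation and favours the small end of the range. In two of the three scenarios the gain in true SD is slight (2.21 to 2.18 and 3.17 to 3.05 msec). All of this stands and limits the priority. It does not justify leaving out a covariate that is already in hand, because the plan also asks for predicted ddQTcF with a CI at each dose, and those predictions carry the offset.

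A reader might infer more than the document supports:

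- *That the placebo imbalance widens the CI.* It does not. The placebo mean is subtracted as a fixed number, so the imbalance moves the estimate and leaves the model CI unaware of it. The widening comes only from variation among active subjects.
- *That the interval's main fault is excess width.* On balance it is much too narrow, and the baseline term does not cure that.
- *That the secondary slope criterion is compromised.* A constant offset leaves the slope alone; only imbalance between dose groups can move it.
- *That the 10 msec conclusion is at risk.* That rule belongs to the primary model, which has the baseline term.
- *That predictions may be off by about 6 msec.* That is the SE of the raw baseline difference, before multiplying by (1 − r).

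**Conclusion.** The concern holds in limited form. Both secondary models lack the baseline adjustment that the primary model has. As a result, predicted ddQTcF carries a chance offset against placebo with an SD of roughly 0.4 to 3 msec, and the model CI at the 36-mg Cmax is about 1% to 15% wider than with adjustment at the active mean. The primary decision is unaffected, and the placebo offset does not touch the secondary slope criterion.

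These sizes rest on assumed SDs and correlations and on a simplified simulation (random intercept only, known variances), so they show scale and are not forecasts. The larger weakness of the same interval, that it treats the placebo mean as known, is separate and would remain after this change. Priority is low to moderate.

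**What to change.** 1. Add baseline QTcF, centred at the placebo-group mean baseline, to both secondary MODEL statements.
2. Evaluate the predictions and CIs at the centred value of zero, for example with an ESTIMATE statement or scoring rows. The term alone is not enough: evaluated at the active mean, all of the placebo imbalance stays in the prediction, and at the mean of all 60 subjects about 5/6 of it stays (50/60).
3. To address the under-coverage, carry the placebo uncertainty through. One way is a subject-level bootstrap that resamples placebo as well as active subjects and, in each resample, re-forms ddQTcF and recomputes the centring value.
4. If the sponsor prefers the unadjusted models, state why, and say that their predictions are not baseline-adjusted.

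Steps 1 and 2 cost one covariate in two statements plus the prediction rows, with no new data. Step 3 needs some programming; the plan already bootstraps the primary analysis. Made before the blind is broken, the change remains a priori under SAP Section 4; made later, it would have to be labelled post hoc.

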- d. Continuous 12-lead ECG data will be obtained using a Mortara continuous 12-lead digital ECG recorder, with triplicate 10-second ECG recordings (approximately 1 minute apart) extracted at the following time points: Baseline (before dosing on Day 1) and at 0.5, 1, 2, 3, 4, 5, 6, 8, 12, 24, 36, 48, 60, and 72 hours after dosing.
- e. Vital signs (supine blood pressure, heart rate, respiratory rate, and oral body temperature) will be measured after the subject has rested for approximately 5 minutes.
- f. Blood samples will be collected for PK assessments at Baseline (0 hour; within 15 minutes before dosing) and at 0.5, 1, 2, 3, 4*, 5, 6, 8, 12*, 24*, 36*, 48, 60*, and 72 hours after dosing, and on Days 8, 15, and 22. (* Planned time points for analysis of moxidectin metabolite concentrations, 8-mg cohort only)

- g. Feces samples will be collected for PK assessments before dosing (single predose collection*) and each bowel motion during confinement in the clinical research unit. Samples will be pooled at the central laboratory for intervals of 0 to 24, 24 to 48, and 48 to 72 hours after dosing (up to 4 samples). (* Feces specimens [the whole bowel movement] may be collected by subjects [at home] within 2 days of submitting them to study staff on Day -1. Collection instructions will be provided at Screening.)
- h. Urine samples will be collected for PK assessments before dosing (single predose collection; first void sample in the morning is acceptable and volume recording is not required) and for pooled intervals of 0 to 24, 24 to 48, and 48 to 72 hours after dosing (4 samples).

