8.1 Continuous 12-Lead Electrocardiogram Assessments

Pharmacodynamics will be assessed via ECGs obtained using a Mortara continuous 12-lead digital ECG recorder, which will be reviewed and analyzed by the central ECG laboratory. The device will remain connected to the subject during the confinement period. The ECG data will be transmitted wirelessly to the Surveyor system, which will extract triplicate 10-second ECG recordings (approximately 1 minute apart) at baseline (before dosing) and at 0.5, 1, 2, 3, 4, 5, 6, 8, 12, 24, 36, 48, 60, and 72 hours after dosing. A window of ± 5 minutes around each time point will be utilized to capture ECGs of adequate quality, although every effort should be made to capture them as close to the scheduled time points as possible. The ECG extractions will be time-matched to the PK samples but obtained before the actual sampling time to avoid changes in autonomic tone associated with the psychological aspects of blood collection as well as the reduction in blood volume subsequent to blood collection.

The continuous ECG data will be sent to the central ECG laboratory for a high-resolution measurement of the cardiac intervals and morphological assessment. The ECG core laboratory staff will be blinded to treatment, time, and study day identifiers.

The 12-lead continuous digital ECG signal for each subject will be recorded continuously during subject confinement.

Digital ECGs will be transmitted to the central ECG laboratory's validated data management system. If targeted ECG time points are artifactual and of poor quality, the central ECG laboratory will extract analyzable 10-second ECGs as close as possible to the targeted time points. The cardiologists responsible for interpreting the ECGs will be blinded to all study drug identifiers and collection times.

Lead II is the lead of choice for the over-reads and the baseline and on-treatment ECGs will be based on the same lead. All ECGs from a particular subject will be read by a single reader.

If lead II is not analyzable, ECG analysis will be conducted in lead V₅. If lead V₅ is not analyzable, the most appropriate lead will be used (eg, lead V₂).

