8.2 General Summaries

All continuous 12-lead ECG data collected will be presented in data listings. Data from subjects excluded from the analysis populations will be presented in the data listings, but not included in the calculation of summary statistics. For categorical variables, frequencies and percentages will be presented. Continuous variables will be summarized using descriptive statistics (n, mean, SD, 2-sided confidence bounds [90% for the QTcF interval or 95% for other parameters], median, 25th percentile, 75th percentile, minimum, and maximum). The mean of the triplicate 0-hour time point on Day 1 will be used as the

baseline. The continuous 12-lead ECG parameters (QTcF, HR, PR, RR, and QRS) and the corresponding changes from Baseline (denoted as dQTcF, dHR, dPR, dRR, and dQRS) and placebo-adjusted endpoints (denoted as ddQTcF, ddHR, ddPR, ddRR, and ddQRS) will be summarized by treatment and time point.

The means and 90% CIs for the dQTcF and placebo-adjusted (algebraic) ddQTcF will be calculated across all subjects for each time point and each active treatment and displayed graphically. Secondary endpoints will also be displayed using 95% CI, if applicable.

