- dQTcF > 30 and ≤ 60 msec;
- dQTcF > 60 msec.

Categorical Analysis of Other ECG Intervals

Categorical summaries of outliers will be provided for other ECG variables (PR, QRS, and HR) as follows:

- PR outliers postdose (PR >200 msec and a 25% or greater increase from Baseline);
- QRS outliers postdose (QRS >100 msec and a 25% or greater increase from Baseline);
- HR outliers postdose (HR <50 beats/minute and a 25% or greater decrease from Baseline);
- HR outliers postdose (HR >100 beats/minute and a 25% or greater increase from Baseline).

Any instance in 1, 2, or 3 of the triplicate ECGs of any subject overall and at each time point will be counted as 1 outlier event.

ECG Diagnostic Statement Analysis

Abnormal diagnostic statements will be tallied and tabulated for each treatment and time point. The variety of diagnostic statements with the same meaning will be aggregated into defined categories. For example, T wave inversion and lead V₂ and T wave flattening in lead II will both be categorized as nonspecific T wave abnormality. The incidence rate of diagnostic statements will be tabulated for both predose and postdose assessments, and also tabulated with diagnostic statements categorized as treatment-emergent diagnostic statements (ie, diagnostic statements not present on any baseline assessment). All abnormal ECG diagnostic findings will be listed.

Adequacy of HR Correction

The adequacy of the correction formula will be assessed by determining the linear relationship of QTcF to RR. Adequacy is defined as a population QTcF:RR slope of <|0.045|, and a slope of <|0.045| in at least 50% of individual subjects.

The QT interval with individual correction (QTcI) is mentioned in the International Council for Harmonisation E14 Guidance as an ancillary correction method.

The QTcI, if needed, will be calculated for each subject, using all available QT/RR predose pairs by first determining the slope of each subject's QT:RR relationship using all available predose data. Then QTcI will be calculated from each subject's individual ECG time point QT and RR interval values with the formula: $QTcI = QT + \text{slope} (1000 - RR)$.

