Figure 14.2.2.15	Residual Plots From Secondary Analysis (PK/PD Population)
Figure 14.2.2.16	Scatter Plot and Linear Regression for QTcF Interval vs. RR Interval (ECG Population)

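### Individual QTcI, if it is needed, would take each subject's QT:RR slope from a single predose triplicate (3 pairs, 1 residual df), too few for a reliable individual correction

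*SAP*

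**What the plan says.** Section 8.3 (Adequacy of HR Correction) judges QTcF by its linear relation to RR. The absolute slope must be below 0.045 in the population and also "in at least 50% of individual subjects". The next paragraph notes that QTcI "is mentioned in the International Council for Harmonisation E14 Guidance as an ancillary correction method". QTcI is to be computed only if needed. It "will be calculated for each subject, using all available QT/RR predose pairs by first determining the slope of each" subject's QT:RR relation, and the formula is QTcI = QT + slope × (1000 − RR). No minimum number of pairs, minimum RR spread, pooling or shrinkage is given.

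Three places fix how much predose continuous ECG there is:

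- Section 3.3, Table 2, footnote d: triplicate 10-second recordings, "extracted at the following time points: Baseline (before dosing on Day 1) and at 0.5, 1, 2, 3" and later hours.
- Section 8.1: the system "which will extract triplicate 10-second ECG recordings (approximately 1 minute apart) at baseline (before dosing) and at 0.5" and later hours.
- Section 8.2: "The mean of the triplicate 0-hour time point on Day 1 will be used as the" baseline.

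Section 8.1 also says: "The 12-lead continuous digital ECG signal for each subject will be recorded continuously during subject confinement". No other predose extraction from that recording is scheduled.

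**The concern.** An individual heart-rate correction is only as good as the individual slope behind it. Here a straight line with two parameters is fitted to three points collected over about two minutes at rest, when RR has little room to vary. Because QTcI is linear in the slope, whatever error the slope carries becomes a leftover dependence of QTcI on RR at all 14 postdose times. The data used for the fit cannot reveal this: within the fitted triplicate the leftover slope is zero by construction.

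QTcI is the only other heart-rate correction that the SAP describes for the continuous ECG, so it would be looked at when QTcF is in doubt. A correction this imprecise could then mislead whoever reads it.

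**Working it through.** **Count of pairs, from the SAP.** There are 1 predose and 14 postdose time points, 15 in all. 60 subjects × 15 = 900, which reproduces the number of QTc-PK pairs in Section 3.2. Without the predose point it would be 60 × 14 = 840. The stated total thus agrees with one predose time point per subject. That point is a triplicate, so each subject has 3 QT/RR pairs and 3 − 2 = 1 residual degree of freedom. The two-sided 95% t multiplier with 1 df is 12.7.

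**Slope error.** Assumptions, none of them in the SAP: QT residual SD σ of 3, 5 or 7 msec about the subject's own line; RR SD within the triplicate of 20, 40 or 60 msec; normal RR; independent errors. For a least-squares slope on 3 pairs,

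slope error = (σ / SD_RR) × t₂ / √2, so P(|error| > c) = 2 × P(t₂ > c × √2 × SD_RR / σ).

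The t here has 2 df because the RR spread of the triplicate is itself random. At σ = 5, SD_RR = 40 and c = 0.045, the argument is 0.045 × 1.414 × 8 = 0.509 and the probability is 0.66. A simulation of 200,000 triplicates at this setting also gives 0.66.

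Share of subjects with a slope error above 0.045:

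| QT SD (msec) | RR SD 20 | RR SD 40 | RR SD 60 |
|---|---|---|---|
| 3 | 71% | 49% | 33% |
| 5 | 82% | 66% | 52% |
| 7 | 87% | 75% | 64% |

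The share passes 50% when σ / SD_RR exceeds 0.045 × √2 / 0.8165 = 0.078, that is, at a QT SD of 3.1 msec when RR SD is 40. At 5/40 the median absolute error is 0.125 × 0.8165 / √2 = 0.072, or about 7 msec of QTcI for an illustrative RR shift of 100 msec.

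**More predose pairs, at 5/40.** 4 pairs: 58%. 9 pairs: 34%. 30 pairs: 6%.

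**Against a QTcF that has failed.** Suppose every subject has the same leftover QTcF:RR slope b. QTcI is then worse in the share of subjects whose slope error exceeds b. The same formula with c = b gives:

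| QT SD (msec) | b = 0.08, RR SD 20 / 40 / 60 | b = 0.10, RR SD 20 / 40 / 60 |
|---|---|---|
| 3 | 53 / 27 / 15% | 45 / 20 / 11% |
| 5 | 70 / 46 / 31% | 63 / 38 / 23% |
| 7 | 78 / 58 / 43% | 73 / 50.4 / 35% |

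QTcI is worse in most subjects in 4 of 9 settings at b = 0.08 and in 3 of 9 at b = 0.10 (one of these at 50.4%).

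**A pooled slope.** With one common slope and 60 subject intercepts on 60 × 3 = 180 predose pairs, SE = σ / (SD_RR × √120). At 5/40 this is 5 / (40 × 10.95) = 0.011. If true slopes vary between subjects with SD τ, a subject's distance from the pooled slope has SD √(SE² + τ²(1 + 1/60)). At 5/40 with τ = 0.03 (assumed), 16% of subjects are more than 0.045 away, against 66% with 3 pairs each. The two approaches break even at τ of about 0.10 at 5/40, and at 0.046 at 3/60, the setting most favourable to 3 pairs.

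**The case against.** The strongest objection is lack of consequence. A reader might infer that QTcI would replace QTcF, because it follows directly after the adequacy test. The SAP does not say so: it calls QTcI ancillary and conditional. The primary endpoint, the primary model and the criterion for a negative QT assessment all use QTcF, and Appendix A lists no QTcI output. This objection stands and keeps the point minor.

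A second tempting inference is that QTcI must be worse than the QTcF that has failed. That does not follow either. It depends on how far QTcF failed, and at leftover slopes of 0.08 and 0.10 QTcI is the worse of the two in most subjects in fewer than half of the assumed settings.

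Third, the 0.045 limit is written for estimated QTcF:RR slopes. Setting the error of a QT:RR slope against it borrows a yardstick that the SAP does not apply to QTcI. The percentages also rest on variances that the SAP does not give, and two of the nine settings (3/40 and 3/60) fall below 50%.

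Fourth, the SAP's wording takes in all available predose data. Counting the Screening safety ECG gives a fourth pair, from another type of recording, and lowers the share at 5/40 only from 66% to 58%. The continuous recording might supply more, but no such extraction is planned.

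Finally, a common slope gives up the individual differences that QTcI is meant to capture. This is a real cost.

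**Conclusion.** The concern holds as a minor one, conditional on QTcI being needed. Taken together, the slope rule and the extraction schedule give 3 pairs and 1 residual degree of freedom per subject; that count follows from the SAP alone. How poor the resulting correction would be rests on assumed variances and independent errors: 33% to 87% of subjects with a slope error above 0.045 over the range examined.

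The documents do not support the stronger conclusions that the primary dQTcF result or the 10-msec decision is affected, or that QTcI would generally be worse than a failed QTcF. By the 0.045 measure, a pooled slope does better than 3-pair individual slopes unless true slopes differ between subjects by an SD above about 0.10 at 5/40, or 0.046 at 3/60.

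**What to change.** In Section 8.3 (Adequacy of HR Correction):

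- State that individual QTcI will not be computed from the single predose triplicate.
- State that, if QTcF fails the adequacy check, a population correction will be reported alongside it as a sensitivity analysis: one QT:RR slope with subject intercepts, fitted to the 180 planned predose pairs.
- Add the placebo postdose pairs (10 × 14 × 3 = 420) only with a time-point effect in the model, because Section 8.3 itself warns of circadian change in dQTcF and a subject intercept does not remove it. The precision figures above do not include these pairs.
- Keep individual QTcI only if further predose ECGs are extracted from the existing recording, with a minimum number of pairs and a minimum RR spread set in advance.

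The cost is a few sentences and one small model on ECGs already planned, settled before the blind is broken. The downside is that a common slope ignores between-subject QT:RR differences. The optional extractions add ECG laboratory work and require the recorder to be running long enough before dosing. Table 2, as far as it can be read, draws the continuous ECG from hour 0, but conversion from PDF may have shifted that row.
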